5.3.1 Ocular Toxicity

Due to the known ocular toxicities associated with MEK inhibitors and the potential for toxicity with HCQ, ophthalmic exams will be mandatory for all patients until protocol treatment is discontinued, as indicated in study calendar. In addition, an ophthalmologist should be consulted if changes in vision develop. However, if the visual changes are clearly unrelated to study treatment (e.g., allergic conjunctivitis), then monitor closely as it may be reasonable to defer ophthalmic examination.

Monitor patients for visual signs and symptoms (such as, change in vision, photophobia and eye pain) during therapy. Special attention should be given to retinal findings (e.g., retinal pigment epithelial detachment (RPED) or retinovascular abnormalities (i.e., branch or central retinal vein occlusions (RVO).

The ocular component of this clinical trial will be important in better understanding ophthalmic risk inherent to the drug combination. All key subjective complaints, exam findings and testing

data will be entered into a study specific case report form for analysis and summarization at the conclusion of the trial.

Table 3 Ocular Examination timeline

	Examination components ¹				
Timepoint ²	Comprehensiv e eye exam ³	OCT	10-2 Humphrey visual fields	Fundus photography⁴	Fundus autofluorescence⁴
Baseline ^a	Х	Х	Х	Х	Х
Cycle 2 ^b	Х	Х			
Cycle 7 ^b	Х	Х	Х		
Cycle 13 ^c	Х	Х	Х	Х	Х
Cycle 19 ^c	Х	Х	Х		
Cycle 25 ^d	Х	Х	Х	Х	Х
End of study ^e	Х	Х	Х	Х	Х

Footnotes (1-4):

1- to be performed OU in both eyes.

2- if ophthalmic AE's are reported, an unscheduled exam should be performed including comprehensive exam and if clinically indicated, HVF 10-2, macular OCT, and fundus photos.

3-To assure the ocular safety of the subjects, at each ocular exam visit the Ophthalmology sub-Investigator will perform a comprehensive eye examination of both eyes. The specified assessments within the ophthalmic examination are reflective of consensus guidelines [American Academy of Ophthalmology Preferred Practice Patterns Committee, 2005] and will be performed according to the Investigator's usual practice in addition to the assessment of visual acuity in the study and will include:

-Ocular alignment and motility, pupillary function, and visual fields by confrontation

-External examination of the eyelids and eyelashes

-Slit-lamp biomicroscopic examination of the anterior segment structures: eyelid margins, conjunctiva, sclera, cornea, anterior chamber, iris, lens, and anterior vitreous

-Intraocular pressure (IOP) measurement

-Following dilation of the pupil, continued slit-lamp biomicroscopic examination of anterior segment structures with clinical grading of lens opacity

-Fundus slit-lamp biomicroscopic examination, including use of accessory diagnostic lenses, to view the vitreous, retina, macula, vasculature, and optic nerve

4-if changes on exam or ancillary testing are noted, fundus photography and autofluorescence should be utilized if clinically indicated.

Footnotes (a-e)

- **a-** Within 56 days of starting therapy
- **b-** +/- 1 week to allow for scheduling difficulties
- c- +/- 2 weeks to allow for scheduling difficulties
- d- After 2 years patients will continue to be followed every six cycles (months). At the half-year follow-ups (e.g. 2.5 y, 3.5 y, etc), exams will comprise the same components as the 1.5 y exam. At the annual follow-ups (e.g. 3y, 4y, etc), the exam will comprise the same components as the 2 year exam.
- e- If end of study occurs within 3 cycles (months) of the most recent scheduled exam, no additional testing is required unless ophthalmic concerns played a role in discontinuation in which case a full end of study exam is conducted. If end of study falls outside of this timeframe, the end of study eye exam should be captured when feasible.

CTCAE Grade ^a	Adverse Event Management	Action and Dose Modification
Grade 1 ^b	 Consult ophthalmologist within 7 days of onset 	 If dilated fundus examination cannot be performed within 7 days of onset, interrupt binimetinib and hydroxychloroquine until RVO, and visual field deficit can be excluded by retina specialist/ophthalmologist.
		 If and RVO excluded, continue (or restart) binimetinib and HCQ at same dose level
		If RVO diagnosed: Permanently discontinue binimetinib and report as SAE.
Grade 2 and Grade 3	 Consult ophthalmologist immediately Interrupt binimetinib and HCQ. 	 If RVO excluded, restart binimetinib and HCQ at same dose level.
		If RVO diagnosed: Permanently discontinue binimetinib and report as SAE
Grade 4	Consult ophthalmologist immediatelyInterrupt binimetinib and HCQ.	• If visual field deficit and RVO excluded, may consider restarting binimetinib at same or reduced dose after discussion with study medical monitor
		 If RVO or visual field deficit diagnosed, permanently discontinue binimetinib and report as SAE.

Table 4 Management and Dose Modification Guidelines for Visual Changes and/or Ophthalmic Examination Findings

Abbreviations: RPED = retinal pigment epithelial detachment; CTCAE = Common Terminology Criteria for Adverse Events; RVO= retinal vein occlusion; SAE = serious adverse event

- a. Refers to CTCAE Version 5.0 'Eye disorders Other, specify'
- b. If visual changes are clearly unrelated to study treatment (e.g., allergic conjunctivitis), monitor closely but ophthalmic examination is not required.

Table 5 Recommended dose modifications for binimetinib for retinal pigment epithelial detachments (RPED)

CTCAE Grade	A	ction and Dose Modification
Grade 1 RPED (Asymptomatic; clinical or diagnostic observations only)	•	Continue treatment with retinal evaluation each cycle (monthly) until resolution. If RPED worsens follow instructions below
Grade 2-3 RPED (Symptomatic with	•	Interrupt binimetinib and hydroxychloroquine
mild to moderate	•	Retinal evaluation each cycle (monthly)
decrease in visual acuity; limiting instrumental ADL)	•	If improved to ≤ Grade 1, restart binimetinib at lower dose or discontinue in patients taking lowest dose

Table 6 Management of Ocular Toxicities

Ocular Toxicity	Uveitis, conjunctivitis	Retinal Vein occlusion, retinal pigment epithelial detachment (RPED), papilledema.	Visual field deficits
Action	Continue all therapies as long as effective local therapies can control inflammation	See table 3, 4, 5	Discontinue HCQ

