5.3 Toxicities and Dose Modifications

Guidelines for specific toxicities are outlined below, but general guidelines for toxicities not listed are provided in Table 5. Of note, if a toxicity is attributable only to one of the investigational drugs, the other investigational agent can be continued if tolerated.

General Dose modification guidelines for binimetinib for toxicities attributable to only binimetinib. These are general guidelines but for specific toxicities dose modification instructions may be different Doses of binimetinib should be adjusted for AEs throughout the study (see Table 1 Recommended Dose Levels). In general, doses should not be reduced or interrupted for Grade 1 AEs unless the AE is a specific ocular AE referred to in the Recommended Dose Modifications Table (see Table 2) but treatment to control symptoms should be provided as appropriate, if applicable.

An individual patient may have their dose of binimetinib reduced to the dose levels in Table 1 below:

Table 1 Recommended Dose Levels

	Binimetinib (mg BID)
Starting Dose	45
Dose Level -1	30
Dose Level -2	15

The lowest recommended dose level of binimetinib is 15 mg BID. When the AE that resulted in a dose reduction improves to and remains stable at the patient's baseline level for a minimum of 14 days, the dose can be re-escalated to the next dose level at the discretion of the Investigator, provided there are no other concomitant toxicities that would prevent drug re-escalation. There is no limit to the number of times the patient can have their dose reduced or re-escalated, however:

- No dose re-escalation of binimetinib is allowed after a dose reduction due to LVEF dysfunction
- No dose re-escalation of binimetinib is allowed after a dose reduction due to retinal toxicity ≥ Grade 2.

Please refer to Dose Modification Table for recommended dose modifications for binimetinib, if applicable, based on the occurrence of treatment-related AEs.

Table 2 Recommended Dose Modifications

In all cases except retina disorders, HCQ may be continued at the discretion of the treating physician

Severity of Adverse Event	Dose Modifications		
Cardiomvopathv			
Asymptomatic, absolute decrease in LVEF of > 10% from baseline that is also	Withhold binimetinib for up to 4 weeks, evaluate LVEF every 2 weeks.		
below the LLN	Resume binimetinib at a reduced dose if the following are present:		
	 LVEF is at or above the LLN and Absolute decrease from baseline is 10% or less and 		

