	Patient is asymptomatic.		
	If LVEF does not recover within 4 weeks permanently discontinue binimetinib.		
Grade 3-4 (Symptomatic congestive heart failure or absolute decrease in LVEF of > 20% from baseline that is also below LLN)	Permanently discontinue binimetinib. Closely monitor LVEF until resolution or up to 16 weeks.		
Venous Thromboembolism			
Uncomplicated DVT or PE	Withhold binimetinib.		
	 If improves to Grade 0-1, resume at a reduced dose. 		
	 If no improvement, permanently discontinue binimetinib. 		
Life threatening PE	Permanently discontinue binimetinib.		
Serous Retinopathy			
Symptomatic serous retinopathy/ Retinal pigment epithelial detachments	 Withhold binimetinib for up to 10 days. If improves and becomes asymptomatic, resume at the same dose. If not improved, resume at a lower dose level or permanently discontinue binimetinib. 		
Retinal Vein Occlusion (RVO) Any Grade	Permanently discontinue binimetinib.		
Uveitis			
Grade 1-3	If Grade 1 or 2 does not respond to specific ocular therapy, or for Grade 3 uveitis, withhold binimetinib for up to 6 weeks.		
	 If improved, resume at same or reduced dose. If not improved, permanently discontinue binimetinib. 		
Grade 4	Permanently discontinue.		

Severity of Adverse Event	Dose Modifications			
Other Eye Disorders (i.e., Non-retinal Eve	ents, non-Uveitis Events			
Grade 1-2	Maintain dose level of binimetinib and increase			
	frequency of ophthalmic monitoring to at least			
	every 14 days until stabilization or resolution.			
Grade 3	Interrupt dosing of binimetinib and refer patient to			
	ophthalmologist within 7 days.			
	• If resolved to Grade ≤ 1 in ≤ 21 days, resume			
	treatment at 1 reduced dose level of			
	binimetinib.			
	 If not resolved to Grade ≤ 1 in ≤ 21 days, 			
	permanently discontinue binimetinib and close			
	follow-up with ophthalmic monitoring until			
	stabilization or resolution.			
Grade 4	Permanently discontinue binimetinib and			
	immediate follow-up with ophthalmic monitoring			
	until stabilization or resolution.			
Interstitial Lung Disease				
Grade 2	Withhold binimetinib for up to 4 weeks.			
	• If improved to Grade 0-1, resume at a reduced			
	dose.			
	• If not resolved within 4 weeks, permanently			
Orada 2 an Orada 4	discontinue.			
Grade 3 of Grade 4	Permanentiy discontinue.			
Hepatotoxicity				
Grade 2 AST or ALT increased	Maintain binimetinib dose.			
	If no improvement within 2 weeks, withhold			

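### Tables 2 and 4 give incompatible dosing instructions for the same non-retinal, non-uveitis eye event at grades 2, 3 and 4, Table 6 conflicts with Table 2 on grade 3-4 uveitis, and no text says which table governs

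*Combined protocol and SAP*

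**What the plan says.** Section 5.3 introduces its binimetinib rules as "General Dose modification guidelines for binimetinib for toxicities attributable to only binimetinib" and adds: "These are general guidelines but for specific toxicities dose modification instructions may be different". Table 2 then has a row for eye disorders that are neither retinal nor uveitis. At grades 1-2 that row begins "Maintain dose level of binimetinib and increase", the increase being in the frequency of eye monitoring. At grade 3 it interrupts binimetinib and sets a condition for restart, "If resolved to Grade ≤ 1 in ≤ 21 days, resume", at one dose level lower. Failing that, binimetinib is permanently discontinued. At grade 4 it is permanently discontinued outright.

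Table 4 in section 5.3.1 covers visual changes and ophthalmic examination findings. A footnote ties its grades to the residual CTCAE term for eye disorders not listed elsewhere. At grades 2 and 3 both drugs are interrupted, and the next step is "If RVO excluded, restart binimetinib and HCQ at same dose level". At grade 4 both are interrupted. If visual field deficit and RVO are excluded, the investigator "may consider restarting binimetinib at same or reduced dose after discussion with study medical monitor".

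Uveitis has its own row in Table 2. Binimetinib is withheld when grade 1 or 2 uveitis fails to respond to ocular therapy, "or for Grade 3 uveitis, withhold binimetinib for up to 6 weeks", and is permanently discontinued at grade 4. Table 6 deals with uveitis and conjunctivitis in one cell with no grade limit: "Continue all therapies as long as effective local therapies can control inflammation".

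**The concern.** One eye event can fall within the scope of two tables that prescribe different things. Two investigators, or one investigator on two occasions, could both comply fully with the protocol and yet differ on whether to interrupt, at what dose to restart, whether recovery must come first, and whether binimetinib stops for good.

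What is at stake is patient safety in an area the protocol itself singles out. Section 5.3.1 makes eye examinations mandatory because of known MEK-inhibitor ocular toxicity, and gives understanding the combination's ophthalmic risk as an aim of the trial. Safety and tolerability are also a primary objective. If drug exposure after an eye event depends on which table was opened, dose modifications and later ocular findings become harder to interpret.

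**Working it through.** The plan states no figure on this point. The check is a grade-by-grade comparison, followed by a search for a rule of precedence.

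**Step 1. Is there overlap?** Take an eye event that is neither retinal nor uveitis, with RVO and visual field deficit excluded. It fits Table 2's row for other eye disorders. It also fits Table 4, whose title takes in any visual change or examination finding. Table 4's grade 1 footnote gives allergic conjunctivitis as an example of what may be excused from examination when clearly unrelated to treatment. That is a non-retinal event, so the table's scope is not confined to the retina.

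**Step 2. Table 2 against Table 4 for that event.**

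| Grade | Table 2 | Table 4 | Result |
|---|---|---|---|
| 2 | Binimetinib maintained; more frequent monitoring | Immediate consultation; both drugs interrupted, then restarted at the same dose | Conflict on interruption; final dose level the same |
| 3 | Interrupted; referral within 7 days; one level lower if grade 1 or less within 21 days, otherwise permanent stop | Immediate consultation; both drugs interrupted, then restarted at the same dose; no resolution condition in the table | Both interrupt; restart dose and restart condition incompatible |
| 4 | Permanent stop | Immediate consultation; both drugs interrupted; binimetinib restart at same or reduced dose may be considered after discussion with the medical monitor | Stop required against restart permitted |

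Grade 1 is not part of the point. Both tables end at the same dose, and Table 4 adds a hold only if the dilated examination cannot be done within 7 days.

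**Step 3. HCQ.** The line above Table 2 lets HCQ continue at the physician's discretion except in retina disorders. Table 4 interrupts HCQ at grades 2, 3 and 4. For a non-retinal event these differ at all three grades.

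**Step 4. Table 2 against Table 6 for uveitis controlled by local therapy.** Grades 1-2 agree: both continue. At grade 3, Table 2 withholds and Table 6 continues. At grade 4, Table 2 stops permanently and Table 6 continues. The conflict is therefore at two grades only.

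**Step 5. Size at grade 3.** From Table 1, the starting dose is 45 mg BID and one level down is 30 mg BID. The difference is (45 - 30)/45 = 1/3. This applies to a first reduction from the starting dose. If the event has not reached grade 1 or less by day 21, Table 2 gives a permanent stop and Table 4 a same-dose restart once RVO is excluded.

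**Step 6. Does any text settle precedence?** Section 5.3 says that instructions for specific toxicities may differ from the general ones. Table 2's eye rows are themselves specific, and the same section points to Table 2 for specific ocular events. The sentence after Table 2 urging caution names no table. No governing table is stated.

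**The case against.** The best defence is a staged reading. Table 4 looks like a rule-out procedure: consult, interrupt, exclude RVO or visual field deficit. Those are its only diagnostic branches, and its grade 1 row calls for a dilated fundus examination. Table 6 sends only RVO, retinal pigment epithelial detachment and papilledema to Tables 3 to 5. Section 5.3 presents its binimetinib guidance as being for toxicities attributable to that drug alone. On this view, Table 4 handles retinal suspicion and Table 2 takes over afterwards. The reading is reasonable and may be what was meant, but it is not written down. Table 4's title and footnote are broad, it has no attribution limit, and it gives its own restart instruction after RVO is excluded.

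Two general safeguards exist. The sentence after Table 2 asks investigators to be cautious where treatment-related toxicity is possible. Section 5.2 takes a patient off treatment if a treatment-related toxicity has not resolved within 28 days, unless the medical monitor grants an exception. Both soften the consequences. Neither chooses between the tables, and Table 4 itself requires no recovery before restart.

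Several stronger readings might be inferred, and the documents do not support them:

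- That the tables conflict for every event other than retinal pigment epithelial detachment. For RVO, Tables 2 and 4 agree that binimetinib is permanently discontinued.
- That the actions are opposite at every grade. At grade 3 both tables interrupt, and at grade 4 Table 4 only permits a restart to be considered.
- That Table 6 conflicts with Table 2 at all grades of uveitis. It does so only at grades 3 and 4.
- That the primary safety result is biased. Section 11.5 tabulates the worst grade and the rate of grade 3 or higher toxicity. The index eye event is graded before any dose action is taken. Only later exposure could change, and no effect on the estimate can be shown from the documents.
- That sites will diverge. This is a single-centre study, so any variation is between investigators or occasions.

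**Conclusion.** The inconsistency is real and should be corrected. Tables 2 and 4 give incompatible instructions at three grades (2, 3 and 4) for non-retinal, non-uveitis eye events with RVO and visual field deficit excluded. They differ on HCQ at the same three grades, and on referral urgency at grade 3. Tables 2 and 6 conflict at two grades (3 and 4) for uveitis that local therapy controls. The sharpest contrasts are an unresolved grade 3 event (permanent stop against same-dose restart) and a grade 4 event (permanent stop against restart allowed).

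The conclusion rests on reading the table titles, row labels and footnote as they stand, and on the absence of any stated precedence. How many patients would be affected is unknown, because the documents give no rate for such events. Mandatory examinations for all 10 to 29 patients show who is monitored, not who will have an event. The conclusion takes no position on which clinical action is right.

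**What to change.** In one amendment, reconcile the ocular rules of Tables 2, 4 and 6 so that each event type and grade has a single action for binimetinib, a single action for HCQ and a single referral urgency. State explicitly which table governs. The sponsor, the medical monitor and the ophthalmology sub-investigator should decide which action stands; no dose rule is proposed here.

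The change edits existing tables and needs no new visits, tests or patients. Its cost is the time for amendment review.

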5.3.2 Hydroxychloroquine Dose Reduction

Any AE of \geq Grade 3 and attributed as possibly, probably or definitely related solely to HCQ will result in the dose being held until the AE has resolved to \leq grade 1 or baseline while binimetinib dosing may continue uninterrupted. If the AE resolves, reinstitution of treatment can occur but at a reduced dose as described in Table 5. If the AE recurs at the reduced dose, treatment will be held until the AE has resolved to \leq grade 1 and when resolved treatment can be reinstituted at the next lower dose level. No more than 2 dose reductions are allowed during the maintenance cycles.

Toxicities that may be attributable to HCQ include: nausea, anorexia, vomiting, constipation, diarrhea, rash, and visual field deficit. If any of these AEs occur at grade ≤ 2 , HCQ may be continued and the AE managed with supportive care. For any AE with a grade ≥ 3 , HCQ dose will be held until the toxicity resolves to \leq grade 2, after which HCQ may be restarted at a reduced dose as described in table 5. With particular regard to visual field deficits patients should be cautioned to report any visual symptoms, particularly difficulty seeing entire words or faces, intolerance to glare, decreased night vision, or loss of peripheral vision. These symptoms of retinal toxicity or subclinical evidence of retinal toxicity on scheduled eye exams should prompt drug discontinuation and ophthalmologic evaluation.

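### Section 5.3.2 requires a reduced HCQ dose that the protocol never gives, sets two recovery grades for the same solely HCQ-related event, and words its visual field rule inconsistently

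*Combined protocol and SAP*

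**What the plan says.** Section 5.3.2 has two paragraphs.

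The first covers adverse events of grade 3 or higher judged "possibly, probably or definitely related solely to HCQ will result in the dose being held until the AE has resolved to" at most "grade 1 or baseline while binimetinib dosing may continue uninterrupted". After that, "reinstitution of treatment can occur but at a reduced dose as described in Table 5". If the event recurs, HCQ is held again and "when resolved treatment can be reinstituted at the next lower dose level". There is a cap: "No more than 2 dose reductions are allowed during the maintenance cycles".

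The second paragraph opens with a list: "Toxicities that may be attributable to HCQ include: nausea, anorexia, vomiting, constipation, diarrhea, rash, and visual field deficit". When one of these is grade 2 or lower, "HCQ may be continued and the AE managed with supportive care". For every adverse event of grade 3 or higher, with no limit by attribution, HCQ is held to at most "grade 2, after which HCQ may be restarted at a reduced dose as described in table 5". The paragraph then turns to visual field deficits and closes by saying that symptoms or subclinical signs of retinal toxicity should lead to stopping the drug and to an eye evaluation.

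Elsewhere, Section 4.1 starts HCQ at 400 mg twice daily and refers the reader to Sections 5 and 6 for dose modifications. Section 4.2 gives a 200 mg tablet strength and 12-hourly dosing. Section 5.3 cites Table 5 for general guidance on unlisted toxicities. Table 5 itself is about binimetinib in retinal pigment epithelial detachment (RPED). Table 6 stops HCQ for visual field deficits, with no grade limit.

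**The concern.** This is a safety dosing rule in a trial where safety and tolerability form a primary objective (Section 1.1). Three instructions cannot be followed consistently as written.

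- At restart, the investigator must reduce HCQ but is not told to what dose. Two patients with the same event can be restarted at different doses, which works against the aim of uniform dosing in Section 4.1. Section 10.4 lists dosing errors among the deviations that require submission; without a stated level, nobody can say whether a given restart dose was an error.
- For a grade 3 event due to HCQ alone, an investigator who restarts at grade 2 complies with one paragraph and breaches the other.
- For a visual field deficit, one sentence lets HCQ continue and others stop it. Section 2.4 names retinopathy as the most predictable cumulative toxicity of chloroquine, the parent compound.

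**Working it through.** The protocol states no figure to reproduce here, so the check is a comparison of texts plus a short dose count.

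**1. Is a reduced HCQ dose given anywhere?**

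- Table 1: binimetinib levels only (45, 30, 15 mg twice daily).
- Table 2: binimetinib modifications; its heading leaves HCQ to the treating physician except in retinal disorders.
- Table 3: eye examination schedule.
- Table 4: visual changes; HCQ is interrupted, then restarted at the same dose.
- Table 5: binimetinib in RPED; HCQ appears only as interrupted.
- Table 6: ocular toxicities; continue or stop, no dose.
- Tables 7 and 8: blood collection and best response.
- Sections 4.1, 4.2 and 6.1: starting dose, tablet strength, product details.

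Result: 0 of 8 tables and no section give a reduced HCQ dose.

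References to Table 5: Section 5.3 (1) + Section 5.3.2 (2) + Table 6 (1) = 4. Only the one in Table 6 points to what Table 5 holds, so 3 of 4 are wrong.

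**2. Which doses could be meant?**

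Inputs: 400 mg twice daily (Section 4.1), 200 mg tablets and 12-hourly dosing (Section 4.2). Assumption: whole tablets, a dose at both times, neither dose above 400 mg.

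- Start: 2 × 400 = 800 mg/day.
- 400 + 200 = 600 mg/day; cut (800 − 600)/800 = 25%.
- 200 + 200 = 400 mg/day; cut (800 − 400)/800 = 50%.

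Only one sequence then gives two reductions: 800 to 600 to 400. If the first step goes to 400, nothing is left for the second.

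If a single 200 mg dose per day is also allowed, 200 mg/day is a third level, cut (800 − 200)/800 = 75%. The two-step sequences become 600 then 400, 600 then 200, and 400 then 200: three instead of one.

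**3. Where do the two recovery grades meet?**

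| Event | First paragraph | Second paragraph | Conflict |
|---|---|---|---|
| Grade 3 or higher, solely HCQ | grade 1 or lower, or baseline | grade 2 or lower | yes |
| Grade 3 or higher, not solely HCQ | silent | grade 2 or lower | no |
| Listed event, grade 2 or lower | silent | HCQ may continue | no |

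Example: a grade 3 rash due to HCQ alone, in a patient with no rash at baseline, improves to grade 2. The second paragraph permits restart; the first still holds the drug. Waiting for grade 1 satisfies both. The gap is one grade.

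**4. Visual field deficit**

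- List in Section 5.3.2, grade 2 or lower: HCQ may continue.
- General rule in Section 5.3.2, grade 3 or higher: restart at a reduced dose.
- End of the same paragraph: retinal toxicity leads to stopping.
- Table 6: HCQ stopped, no grade limit.
- Table 4, grade 2 or 3 visual changes: HCQ restarts at the same dose once retinal vein occlusion (RVO) is excluded; a visual field deficit need not be excluded.

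**The case against.** The strongest reply has four parts.

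- **The grade rules can be reconciled.** Read specific over general, solely HCQ-related events wait for grade 1 or baseline, and other events may restart at grade 2. The second paragraph only permits, so holding longer breaks nothing. Section 5.2 also uses grade 2 or baseline as a recovery level. Part of this stands: a reader might infer that the two grades conflict for every grade 3 or higher event, and the text does not support that, because the first paragraph is limited to events due to HCQ alone. Within that group the conflict remains, since the second paragraph carries no exclusion. Section 5.2 does not settle it, because its grade 2 level is set for events that are not treatment-related.
- **Visual field deficit is dealt with in the same paragraph.** It is singled out after the general rule, and the paragraph ends in discontinuation, in line with Table 6. This largely stands. A reader might infer that the protocol directs investigators to keep giving HCQ through a visual field deficit; taken as a whole, it does not. What remains is a drafting conflict.
- **The dose levels can be worked out.** If two reductions must be possible, 600 then 400 mg/day is the only sequence. That holds only under the tablet assumption. Section 4.2 lets the schedule change for gastrointestinal symptoms, and five of the seven listed toxicities concern the gut or appetite, so once-daily dosing is not clearly excluded. The cap is also a maximum, so it does not oblige the first step to leave room for a second.
- **No analysis changes.** This is correct and is accepted.

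**Conclusion.** Section 5.3.2 is wrong as written and should be corrected. The missing HCQ dose levels and the Table 5 citations are the firmest part and need no assumption: the dose is required, the cited table does not hold it, and no other place does. The two recovery grades are a real conflict of one grade, confined to grade 3 or higher events due solely to HCQ. The visual field wording is the weakest of the three.

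The 25% and 50% cuts rest on whole tablets taken every 12 hours. The number of patients affected cannot be derived from the documents.

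A reader might also infer that the efficacy or safety conclusions are compromised. The documents do not support that: the two-stage response rule in Section 11.4 and the exact interval for the grade 3 or higher toxicity rate in Section 11.5 stand as planned.

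**What to change.** - **Dose levels.** Add an HCQ dose-level table with levels set by the sponsor. One example, on the tablet assumption above, is 800 to 600 to 400 mg/day. Cite it in both paragraphs of Section 5.3.2 in place of Table 5, and correct the Table 5 citation in Section 5.3.
- **Recovery grade.** State that the first paragraph's threshold (grade 1 or lower, or baseline) governs events related solely to HCQ, and limit the second paragraph's grade 2 rule to other events. Alternatively, the sponsor may choose one grade for all events. Imposing grade 1 on every event goes further than resolving the overlap requires.
- **Visual field deficit.** Take it out of the continue/restart rule and refer to Table 6. Table 6 stops HCQ only for visual field deficits, and sends RVO, RPED and papilledema to other tables. Keep the closing sentence of Section 5.3.2 as the source for stopping on retinal toxicity. Align Table 4 so that an HCQ restart after grade 2 or 3 visual changes also requires a visual field deficit to be excluded.

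Cost: a short wording amendment and one three-row table, with no change to sample size, visits or analyses. The downside is longer HCQ holds for patients who might otherwise have restarted at grade 2. Some holds could reach the 28-day limit in Sections 5.2 and 9.4.7, after which the patient comes off treatment unless the medical monitor grants an exception. Section 7.2.1 cites mean half-lives of 30 to 50 days for HCQ-related compounds, so the sponsor should weigh this when choosing the grade.
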